**Surgery:**

The date of surgery or procedure is generally not imputed. If the date of surgery or procedure needs to be imputed for an analysis (e.g., to calculate duration or elapsed time as covariates for efficacy analyses), the rules for imputation will be defined within the algorithm of the derived covariate. Additionally, post treatment surgery or procedure dates maybe imputed (where applicable) to determine date of new anti-cancer therapy. In this case only, the date of new anti-cancer therapy (not specific surgery or procedure date) will be stored on appropriate efficacy datasets. The category for surgical procedure variable, and not any variables that use imputed partial dates, will be used to differentiate prior, on, and follow-up surgical procedure data. The derived time in relation to treatment variables are not needed for reporting of data because the category for surgical procedure variable can be used. Therefore, imputed dates are not needed for derivation of time in relation to treatment.

Dataset	Missing Element	Rule
Surgical Procedures	day, month, and year	
 
No Imputation for completely missing dates
 

	day, month	
 
If partial date contains a year only set to January 1st.
 

	day	
 
If partial date contains a month and year set to the 1st of the month
 

**Concomitant Medication and Blood and Blood Supportive Care Products:**

Impute start and end dates for use in derivation of the reference variables concomitant medication start and end relative to treatment and blood and blood supportive care start and end relative to treatment, but do not permanently store the imputed start and end dates in the analysis datasets. The reference variables will be used to differentiate before, during and after for the concomitant medication or blood or blood supportive care start and end dates. The derived time in relation to treatment variables are not needed for reporting of these data.

Dataset	Date	Missing Element	Rule
Concomitant Medication  Blood and Blood Supportive Care Products	Start Date	day, month, and year	
 
No Imputation for completely missing dates
 

		day, month	
 
If study treatment start date is missing (i.e. subject did not start study treatment), then set start date = January 1.
 
Else if study treatment start date is not missing: 
 
If year of start date = year of study treatment start date then 
 
If stop date contains a full date and stop date is earlier than study treatment start date then set start date = January 1.
 
Else set start date = study treatment start date.
 
 
 
Else set start date = January 1.
 
 
 

		day	
 
If study treatment start date is missing (i.e. subject did not start study treatment), then set start date = 1st of month.
 
Else if study treatment start date is not missing: 
 
If month and year of start date = month and year of study treatment start date then 
 
If stop date contains a full date and stop date is earlier than study treatment start date then set start date = 1st of month.
 
Else set start date = study treatment start date.
 
 
 
Else set start date = 1st of month.
 
 
 

	End Date	day, month, and year	
 
No Imputation for completely missing dates
 

		day, month	
 
If partial end date contains year only, set end date = earliest of December 31 or date of last contact.
 

		day	
 
If partial end date contains month and year, set end date = earliest of last day of the month or date of last contact (MSTONE.LCONTDT).
 

**Time to Event:**

Start dates for follow-up anti-cancer therapy, radiotherapy (where applicable), and surgical procedures (where applicable) will be temporarily imputed in order to define event and censoring rules for progression-free survival, response rate, or duration of response (i.e. start date for new anti-cancer therapy). Dates will only be imputed when a month and year are available but the day is missing. The imputed date(s) will not be stored on the anti-cancer therapy, radiotherapy, or surgical procedure datasets. The following rules will be used to impute the date when partial start dates are present on anti-cancer therapy radiotherapy, and/or surgical procedures dataset[s]:

Dataset	Date	Missing Element	Rule
Anti-Cancer Therapy  Where applicable:  Radiotherapy  Surgical Procedures	Start Date	day, month, and year	
 
No Imputation for completely missing dates
 

		day, month	
 
No imputation for missing day and month (note the eCRF should only allow for missing day)
 

		day	
 
If partial date falls in the same month as the last dose of study treatment, then assign to earlier of (date of last dose of study treatment+1, last day of month).
 
If partial date falls in the same month as the subject's last assessment and the subject's last assessment is PD, then assign to earlier of (date of PD+1, last day of month).
 
If both rules above apply, then assign to latest of the 2 dates
 
Otherwise, impute missing day to the first of the month.
 

	End Date		
 
No imputation for partial end dates will be performed
 

The date of new anti-cancer therapy is derived as the earliest date of new anti-cancer therapy (e.g., chemotherapy), radiotherapy (where applicable), or cancer related surgical procedure (where applicable) and will include imputed dates. If the date of new anti-cancer therapy is an imputed date, then the date of new anti-cancer therapy flag variable is assigned the value of 'D' to indicate that the day portion of the date is imputed (following ADaM convention).

As multiple dates are used to derive the date of new anti-cancer therapy ensure that the date of new anti-cancer therapy flag is only set to 'D' if the derived date is imputed. For example if the date of new radiotherapy is imputed but the date of new anti-cancer therapy is prior to date of new radiotherapy and the new anti-cancer therapy date is not a partial date then the flag should be set to missing as the date used for the new anti-cancer therapy is not an imputed date.

**Covariates:**

If the algorithms for covariates (e.g., prognostic factors) include any partial dates, then the algorithms must specify the date imputation rules used in the derivations. The following imputation rules are the standard rules to be used when algorithms for covariates require date imputations.

Variable	Example of when to impute	Rule
Prior anti-cancer therapy start date  Prior radiotherapy start date	
 
• Impute to derive duration                             
 
○ Duration of prior Therapy
 
 
 
	
 
• Only impute when a month and year are available but the day is missing.
 
• Impute to first day of the month.
 
• Do not store imputed date
 
• Use only for relevant efficacy analyses (i.e. not to be used for general radiotherapy or anti-cancer therapy summaries)
 

Prior anti-cancer therapy end date  Prior radiotherapy end date	
 
• Impute to derive elapsed time and duration                             
 
○ Duration of prior Therapy
 
○ Time from Last dose of prior therapy to Randomization
 
 
 
	
 
• Only impute when a month and year are available but the day is missing.
 
• Impute to last day of the month, also must be prior to 'start'                             
 
○ if 'start' is the first of the month assign to 'start', else assign to 'start'-1), where 'start' is either the date of randomization or the start of study treatment.
 
 
 
• Do not store imputed date
 

Variable	Example of when to impute	Rule
		
 
• Use only for relevant efficacy analyses (i.e. not to be used for general radiotherapy or anti-cancer therapy summaries)
 


Any disease characteristic dates. For example:
 
 
• Date of initial diagnosis
 
• Date of last recurrence
 
• Date of last progression
 
	
 
• Impute to derive elapsed time               
 
○ Time from initial diagnosis to randomization for use as a covariate
 
○ Time from progression on last therapy until randomization for use as a covariate
 
 
 
	
 
• If both month and day are missing, impute to January 1st
 
• else if day is missing, impute to first day of the month.
 
• Do not store imputed date
 
• Use only for relevant efficacy analyses (i.e. not to be used for general disease characteristic summaries)
 

### 9.2.6. Imputation of Missing Exposure End Dates

In general, completely missing dates are not imputed. However, subjects in oncology trials may still be on study treatment when analyses are performed and so may have missing exposure end dates. For subjects still on study medication at the time of data cutoff, the exposure end date will be imputed to the earliest of: the date of clinical cutoff, the date of withdrawal from the study or the death date. The imputed exposure end date will be used to calculate cumulative dose and exposure duration.

### 9.2.7. Baseline Definition

Baseline will be defined as the most recent, non-missing value prior to or on the first study treatment dose date for subjects randomized to the ofatumumab arm. For subjects randomized to the observation arm, baseline will be defined as the most recent, non-missing value prior to or on the randomization date.

For laboratory data, baseline will be defined as the most recent, non-missing value from a central laboratory prior to or on the first study treatment dose date. For subjects randomized to the observation arm, baseline will be relative to the randomization date. If there are no central labs collected for a subject and lab test prior to or on the first dose of study treatment, the most recent, non-missing value from a local laboratory prior to or on the first dose of study treatment (or randomization date for the observation arm) will be defined as the baseline value.

### 9.2.8. Change from baseline

Change from baseline will be presented for safety data as described in Section 12.

Change from baseline is calculated as:

- For records occurring after baseline: (visit value) – baseline value.

Percent change from baseline is calculated as:

- For records occurring after baseline: ((change from baseline) / baseline value) \* 100

If either the baseline or visit value is missing, the change from baseline and/or percent change from baseline is set to missing as well.

### 9.2.9. Multiple Assessments

All data will be reported according to the nominal visit date for which it was reported (that is, no visit windows will be applied during dataset creation). Unscheduled data will only be included in the display sections that report “worst case”.

Data from all assessments (scheduled and unscheduled), including multiple assessments, will be included in listings.

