3.1.4. Follow-up Phase

Survival and disease status assessments (physical examination and evaluation of peripheral blood samples) will be performed post treatment every 3 months for 5 years after last treatment.

A bone marrow examination is required to confirm Complete Remission (CR) at least 2 months after completion of therapy and when a subject fulfills the International Workshop for Chronic Lymphocytic Leukemia (IWCLL) updated National Cancer Institute-Sponsored Working Group (NCI-WG) requirements for Complete Remission (CR) [Hallek, 2008]. Previous results may be used or if not available, a bone marrow exam may be done at screening. If a subject's response improves to a CR while on study, then a bone marrow examination is required to confirm CR at least 2 months after response as per the updated IWCLL NCI-WG requirements for CR [Hallek, 2008].

Additionally, CT Scans are required yearly while on study, including during follow-up, and at disease progression, whenever that may occur.

Subjects demonstrating disease progression will be followed for survival status until study completion. Follow-up assessment after disease progression on treatment will assess survival status, date of next CLL therapy, type of therapy and response to therapy. It is acceptable for the information for survival follow-up visits to be collected remotely (via telephone, email), as necessary. The frequency of the survival follow-up visits should be per local standard of care, suggested every 3 months for CLL. Minimally, this should be collected at least annually.

PRO measures (EORTC QLQ-C30, EORTC QLQ-CLL16, EQ-5D and a Health Change Questionnaire) will be administered for completion by the subject at follow-up visits, as per Section 6.5.6.

Please refer to Section 6: Study Assessments and Procedures for detailed assessment instructions.

Supplementary study conduct information not mandated to be present in this protocol is provided in the accompanying Study Procedures Manual (SPM). The SPM will provide the site personnel with additional administrative and detailed technical information.

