4.4. Withdrawal Criteria

Subjects may be withdrawn from investigational product at any time if it is the wish of the subject (or their legally acceptable representative) for any reason, the investigator judges it necessary due to medical reasons including disease progression or the subject becomes pregnant. (See also Section 8.3.5.) The subject will be evaluated for disease status and survival per the follow-up visit schedule outlined in Section 3.1.4.

Furthermore, a subject may withdraw from study participation (i.e., withdraw consent) at any time for any reason. The reason for withdrawal from study participation must be documented in the eCRF.

The investigator must make every effort to perform and document the following in the eCRF:

- Disease assessment
- Hematology and Chemistry
- Physical examination, vital signs and body weight assessment
- Response Assessment
- AE/SAE Assessment
- Concomitant Medication assessment
- Subject completion of PRO measures (EORTC QLQ-C30, EORTC QLQ-CLL16, EQ-5D and the Health Change Questionnaire)

For data collection purposes, subjects are considered as completing the study if they have died during the treatment or follow-up phases, are lost to follow-up, or withdraw consent.

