6.5.6. Administration of PRO Measures

The EORTC QLQ-C30, EORTC QLQ-CLL16, and EQ-5D should be administered at baseline and at each treatment clinic visits; beginning with Visit 3, and at each follow-up visit post treatment; every 3 months through Month 60. The Health Change Questionnaire should be administered at all the aforementioned post-baseline visits. If a subject demonstrates disease progression, the measures should be completed at the progression visit and again one time after determination of progression. If a subject in PD will be available and willing, post-PD questionnaires may be administered through the date that would correspond to the subject's Month 60 visit. If a subject withdraws from the study then the PRO questionnaires should be administered at the point of withdrawal.

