6.6. Pharmacokinetics

Blood samples will be collected from subjects receiving ofatumumab predose and 0.5 h after the end of the infusion (EOI) at treatment on Month 1 Week1 (Day 1), Month 1 Week 2 (Day 8), Months 3, 7, 13, 19 and 25. In addition, predose samples will be collected prior to ofatumumab administration on Months 5 and 9. A pharmacokinetic sample (and a HAHA sample) should also be obtained at the last treatment visit if it does not occur at a scheduled sampling time (e.g., if treatment is discontinued early). Samples will also be collected at any time of day during clinic visits at 3 and 6 months post-last ofatumumab dose. Table 5 provides the pharmacokinetic sample collection schedule.

Predose samples may be collected at any time prior to dosing, and 0.5 h post-EOI samples may be collected within a \pm 15 minute window around the scheduled time. The actual date and time of each sample collection will be recorded in the eCRF.

Table 5 Ofatumumab pharmacokinetic sample collection schedule

Month	Week	Visit	Sampling time
1	1	1	Predose, 0.5 h post-EOI
1	2	2	Predose, 0.5 h post-EOI
3	9	3	Predose, 0.5 h post-EOI
5		4	Predose
7		5	Predose, 0.5 h post-EOI
9		6	Predose
13		8	Predose, 0.5 h post-EOI
19		11	Predose, 0.5 h post-EOI
25		14	Predose, 0.5 h post-EOI
28		15	3 months after last dose ^{1,2}
31		16	6 months after last dose ^{1,2}

1. Collect sample at any convenient time on study day.

2. Collect sample relative to last dose of ofatumumab regardless of when it occurs

Sample collection, processing, and shipping instructions are provided in the study procedures manual.

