**Summaries and Analyses:**

Changes from baseline scores over time in patient reported B-symptoms score will be analyzed with a repeated measures analysis of covariance (ANCOVA). Analyses will be carried out using PROC MIXED in SAS: baseline score, age group, performance status, and Binet stage, time, treatment, baseline by time, and treatment by time interaction will be fitted as fixed effects, and time will be treated as the repeated variable within subject. Restricted maximum likelihood (REML) will be used to estimate the parameters of the model. An unstructured variance-covariance matrix in the repeated measures model will be used. The model may be modified if required in order to obtain convergence.

Treatment comparisons, including estimated treatment difference, 95% confidence intervals and associated p-values will be provided.

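### Nominal visit labels put early ofatumumab stoppers' follow-up questionnaires at Month 4-26 under the same label as completers' Month 28, and the PRO model does not define time

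*SAP*

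**What the plan says.** **Visit assignment.** SAP 9.2.9 keeps the nominal visit for every record: "no visit windows will be applied during dataset creation". It adds: "Unscheduled data will only be included in the display sections that report" the worst case.

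**Follow-up clock.** Under Protocol 3.1.4, survival and disease status assessments "will be performed post treatment every 3 months for 5 years after last treatment". For a subject withdrawn from investigational product, Protocol 4.4 says: "The subject will be evaluated for disease status and survival per the follow-up visit schedule outlined in Section 3.1.4". Appendix 1 (Time and Events) prints treatment Visits 3-14 at weeks 9-97 (Months 3-25) and follow-up Visits 15-34 at weeks 109-337 (Months 28-85). Table 5 in Protocol 6.6 ties the Month 28 and Month 31 pharmacokinetic rows to the last dose: "Collect sample relative to last dose of ofatumumab regardless of when it occurs". SAP 9.2.12 names the first two follow-up assessments by months of follow-up (3M FU, 6M FU).

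**PRO collection.** Protocol 6.5.6 requires questionnaires at baseline, at each treatment visit from Visit 3, at follow-up visits, at the progression visit and once afterwards. It also says: "If a subject withdraws from the study then the PRO questionnaires should be administered at the point of withdrawal". The withdrawal column of Appendix 1 marks PRO but carries no visit number, week or month.

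**PRO model.** SAP 13.1 fits a repeated measures model with treatment, time, baseline-by-time and treatment-by-time terms and an unstructured covariance matrix, in which "time will be treated as the repeated variable within subject". The other questionnaires use the same model. The section does not say whether time is nominal visit, actual day or time from randomization, or whether follow-up records enter.

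**The concern.** In a randomized comparison of repeated questionnaires, each time point should mean the same elapsed time since randomization in both arms. A follow-up label here means elapsed time since the last treatment. For subjects who complete the two-year phase the two clocks agree. For an ofatumumab subject who stops early without progression they do not, and no rule brings them back together. Observation subjects have no drug to stop, so the displacement can differ by arm.

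If the model's time factor is the nominal visit, two things follow. The ofatumumab mean at each follow-up label blends subjects at different distances from randomization. Early stoppers are also absent from the treatment-phase labels at which, by the calendar, they did complete questionnaires. The treatment-by-time contrasts would then partly reflect when drug was stopped. Quality of life is a stated secondary objective, and these contrasts are the SAP's means of comparing the arms on it.

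The withdrawal questionnaire is a separate gap. It is required and is close to dropout, so it is informative, but the SAP assigns it to no time point.

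**Working it through.** **Inputs.** Dose weeks 1, 2, 9, 17, ..., 97 (Protocol 3.2 and Appendix 1). Follow-up spacing of 3 months from last treatment (Protocol 3.1.4), which is 12 weeks on the Appendix 1 grid. Appendix 1 months are four-week months.

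**Formulas.** Month = (week - 1)/4 + 1. Follow-up visit k falls at week L + 12k, where L is the week of the last dose.

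**Reproducing the printed schedule (L = 97).**
- k = 1: 97 + 12 = week 109; (109 - 1)/4 + 1 = Month 28.
- k = 20: 97 + 240 = week 337; (337 - 1)/4 + 1 = Month 85.

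Both match Appendix 1 for Visits 15 and 34.

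**Same rule for earlier last doses (first follow-up visit, k = 1).**

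| Last dose (week) | First follow-up (week) | Month | Weeks before week 109 |
|---|---|---|---|
| 1 | 13 | 4 | 96 |
| 17 | 29 | 8 | 80 |
| 49 | 61 | 16 | 48 |
| 89 | 101 | 26 | 8 |

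The first follow-up visit therefore falls between Month 4 and Month 26, which is 8 to 96 weeks (2 to 24 four-week months) before the Month 28 position. Because every later visit adds the same 12 weeks, a subject's shift is constant over all 20 follow-up visits.

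**From label to model.** SAP 9.2.9 is the only general rule for placing records in time. The 280-event SAP titles its PRO tables by treatment and visit. An unstructured covariance matrix in practice needs a set of discrete time points shared by all subjects. Together these make nominal visit the natural meaning of time in 13.1, but this remains an inference. SAP 9.2.11 adds actual-treatment-cycle variables to adverse event, blood product, ECG, laboratory and vital sign data; questionnaires are not on that list.

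**Size, by assumption only.** The documents give neither the share of early stoppers nor any drift in scores. Let s be their share of ofatumumab responders at a follow-up label, b the drift in points per month on a 0-100 scale, and d their mean displacement in months. The time-related shift in the ofatumumab mean is s x b x d. With d = 12:
- s = 0.10, b = 0.1: 0.10 x 0.1 x 12 = 0.12 points.
- s = 0.40, b = 0.5: 0.40 x 0.5 x 12 = 2.4 points.

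Its direction depends on the direction of the drift. Any effect of stopping itself is not included.

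**Which outputs remain.** The 280-event SAP drops the change-from-baseline analyses for QLQ-CLL16, QLQ-C30, EQ-5D utility and EQ-5D VAS (4.0020, 4.0070, 4.0170, 4.0220). It keeps the B-symptoms analysis (4.0120) and by-visit PRO summaries, and carries over the interim report's data rules. The final-analysis SAP lists no questionnaire tables.

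**The case against.** The strongest reply is that the problem is mostly missing detail in a small corner of the trial. Much of that stands.

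- A reader might infer that the model sets early stoppers at Month 4-26 against observation subjects at Month 28. The documents do not support that. SAP 13.1 says only time, and ofatumumab completers share the Month 28 cell.
- A reader might also take every progression-free observation subject to be at Month 28. SAP 9.3 gives observation subjects their own date of entry into follow-up, so Month 28 holds only for those observed through Visit 14.
- It is tempting to say that withdrawal and progression questionnaires are discarded. SAP 9.2.9 restricts unscheduled data, whereas withdrawal is a planned column in Appendix 1 and progression may be found at a regular visit. All that is firm is that the withdrawal record has no stated slot.
- The Table 5 footnote governs pharmacokinetic samples. It illustrates the last-dose clock but is not a rule for PRO labels.
- Extending the point to laboratory or immunoglobulin tables is weak. Appendix 1 schedules no immunoglobulins in follow-up, and Protocol 6.3.4 makes those samples optional. Laboratory data have actual-cycle variables, and SAP 9.2.1 anchors safety data to first dose on ofatumumab.
- Subjects who stop for progression have their own questionnaire rule in Protocol 6.5.6.

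What the reply does not remove is that the no-window rule is stated, the follow-up clock is stated, and together they put different elapsed times under one label. If time in 13.1 is not nominal visit, it is undefined for the treatment comparison, and that also needs correcting.

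**Conclusion.** The point holds within a limited scope. The first follow-up visit of an ofatumumab subject who stops early without progression falls at about Month 4 to 26, under the label that completers reach at Month 28, and the shift carries forward. That follows from the documents' own schedule. That the distortion reaches the mixed-model contrasts depends on reading time in SAP 13.1 as nominal visit, which is likely but not stated.

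The affected results are the PRO by-visit summaries and mixed models. SAP 8.4 leaves other secondary endpoints outside the multiplicity control and treats them as nominal, and both later SAPs describe their analyses as descriptive. PFS, overall survival and time to next therapy run on actual dates and are unaffected. The 0.12 to 2.4 points shown in the working is an illustration under assumed shares and drifts, not an estimate; the documents neither establish a bias nor allow it to be sized. This is a cheap improvement to a secondary comparison and does not threaten the trial's main conclusions.

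**What to change.** In SAP 9.2.9 and 13.1, for PRO analyses only:

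- Define time as days since randomization, with analysis windows centred on the 8-weekly and then the 3-monthly schedule. Take the PRO visit targets from Protocol 6.5.6, because SAP 13 still lists Days 1 and 85 for the treatment phase.
- Assign scheduled, withdrawal and progression-visit questionnaires to those windows, and use the windowed time in the 13.1 model and the by-visit PRO summaries.
- State which record is used when two fall in one window, and which window takes a record on a boundary. The boundary rule will be needed often: for most early last doses, the first follow-up visit at L + 12 weeks lies exactly midway between the targets at L + 8 and L + 16.

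Keep nominal labels for listings, keep last-dose timing for pharmacokinetic and HAHA samples, and leave laboratory and immunoglobulin conventions as they are.

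The cost is SAP wording, one derivation from dates already collected, and a rerun of some PRO tables. Some 8-week windows will be empty for early stoppers, who are seen every 12 weeks; those gaps are real and are better shown than relabelled.
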